
#### **Monitoring and Responding to Adverse Events**

All study personnel based in Uganda will be trained in identifying indicators of conditions that may jeopardize the welfare of participants and the limits of confidentiality. This training, conducted by the PI ([name]) and in-country Co-I ([name]) or designee, includes reviewing possible scenarios and knowledge of key questions used to assess risk. Interview staff are trained to err on the side of caution and told to contact the Project co-Coordinators ([name], in Uganda—at [name]; [name] – at [name]), the study collaborating priest from Masaka Diocese ([name]—also in Uganda at [name]), and the in-country Co-I ([name] at [name]) all of whom are always available, by telephone, in the event of the need to break confidentiality due to an instance of mandatory reporting. Under the guidance of in-country Co-I ([name]), the Project Coordinator, and the Collaborating Priest, research staff are trained either to contact the police to ensure safety of participants, or if appropriate, to have emergency personnel take the adolescent to the nearest hospital.

Reporting of adverse events will occur according to a project protocol. For this study, the PI ([name]) and the in-country Co-I ([name]), the Project Coordinator (based in Uganda), and the study coordinators (all based in Uganda) will oversee safety and monitoring of adverse events. This group is expected to meet in-person three to four times per year and will have weekly telephone conference calls. In the case of an adverse event, staff will inform the in-country Co-I, Project Coordinators and the Parish Priest immediately and then the U.S. based PI within 24 hours (with substantial efforts made to also inform the PI immediately) of the presence of a possible unanticipated adverse event. Any presence of a possible unanticipated adverse event will be immediately reported and brought to the attention of the Washington University Institutional Review Board along with the UVRI Research and ethics committee and Ugandan National Council of Science and Technology IRB. The IRBs will determine whether it is appropriate to stop the study protocol temporarily or will provide suggestions and/or modifications for the study procedures. Possible modifications may include adding new risks to the consent form and re-consenting all study participants.

Preliminary outcomes data will be examined quarterly by the PI ([name]) and the Co-Investigators (Drs. [name] and [name]). If preliminary outcome data indicates harmful impact of the study to the participants (the adolescents), the Washington University IRB committee, the UVRI Research and ethics committee as well as the Uganda National Council of Science and Technology, will be notified and it is possible that the study will be discontinued immediately. However, we do not anticipate any negative effects of participating at this time, as much of the proposed intervention has been tested previously in three sets of studies (Suubi Uganda, Suubi-Maka and Bridges) without adverse events. In addition, findings from our earlier studies guiding this application suggest an association with positive outcomes, including participants being able to save and invest in education, active participation by the children, and enthusiasm by the families and local leaders.

It is important to note that [name] (PI) is a Social Worker by Training, and [name] (the in-country Co-I) is a Clinical Medical Doctor. One of the Field Project Coordinators ([name]) is trained clinical psychologist; and the other one, [name] is both a trained Teacher and Social Worker. In addition, the two Field Project Coordinators ([name] and [name]) have extensive professional counseling training and experience. When appropriate this team will be available to speak with those adolescents that experience discomfort with the interview questions and require further attention. In the event that counseling is needed, the project staff will make the appropriate referrals.

#### **Data Management and Integrity to Protect Confidentiality**

To protect the integrity of the participants' data, we will adhere to the following procedures. First, we will use participant data only for the purpose of research. The research team will keep all data confidential. We will not share any information or answers we get from the adolescent participants with their caregivers, classmates, friends, teachers, church leaders, or public officials. Second, the Project Coordinators ([name] and [name]) will assign random code numbers to all adolescents participating in the study. This code number is used on all information collected from participants, including questionnaires and computer-assisted interviews. Since the study is a longitudinal one, we maintain lists of participants with links between identifying information and code numbers. Only the Principal Investigator ([name]), the in-country Co-Investigator ([name]) and the Project Coordinators have access to these lists, which are kept in locked files. Other study personnel have access, on an as-needed basis, to individual participants' names and code numbers in order to adequately perform their duties. For example, interviewers must label the questionnaires with the correct code number of the participant whom they are interviewing. All personnel must complete

required research training before they are granted access to this identifying information. They must complete the Human Subjects Training sponsored by the National Institute of Mental Health, which complies with federal guidelines delineated in 45 CFR Part 46. Personnel must also sign confidentiality statements that specify that if the participants' confidentiality is breached unintentionally, that personnel will follow the procedures for reporting this breach to the Principal Investigator. The confidentiality statements also state that unintentional or deliberate violations of participants' confidentiality may result in demotion or termination, depending upon the severity of the event. The project personnel also participate in training with the Principal Investigator, in-country Co-Investigator ([name]) and/or Project Coordinators regarding data safety, confidentiality of participants, limits of confidentiality, and proper administration of the study protocol. We will store all hard copies of data in locked cabinets to which only the PI, the in-country Co-Investigator, and Project Coordinators have access. After completion of an interview with a study participant, data with code numbers is placed in a separate locked filing cabinet only to be retrieved for entry. After research assistants enter data into password protected computer files, only the PI, the in-country Co-Investigator, and the Project Coordinators, and data entry assistant will have access to these files.

## **Data Analysis Plan and Statistical Procedures**

Primary analyses for Specific Aim 1. For Specific Aim 1, *Examine whether the Suubi4Her intervention is effective in protecting adolescent girls against known HIV risk factors*, we hypothesize that following baseline participants in:

- 1. H1A: YDA will have lower odds of STIs and HIV risk behaviors vs. control participants;**
- 2. H1B: YDA+MFG will have lower odds of STIs and HIV risk behaviors vs. control participants, and**
- 3. H1C: YDA+MFG will have a lower odds of STIs and HIV risk behaviors vs. YDA participants.**

Our primary interest is to estimate the marginal or population-average effects of intervention participation on HIV risk outcomes rather than the effect for a hypothetical average subject or school. Moreover, within-subject and within-school HIV risk outcome correlations are considered nuisance parameters rather than quantities of interest to be modeled explicitly. Accordingly, generalized estimating equations (GEE) will be used to perform the proposed primary analyses to test Hypotheses H1A-H1C. These hypotheses will be tested by three pairwise planned time-averaged comparisons of post-baseline measurements. Alpha ( $\alpha$ ) will be set at  $.05/3=.017$  for these three planned comparisons to maintain a nominal  $\alpha=.05$ . Any additional post-hoc comparisons (e.g., paired comparisons of groups at each time point) will maintain nominal alpha of .05 through the use of simulation-based stepdown multiple comparison methods. The alternating logistic regression (ALR) approach implemented in SAS PROC GENMOD will be used to address the 3-level clustering of observations within participants and participants within schools. Though GEE estimates are consistent even if the correlation structure is misspecified, GEE's statistical efficiency improves as the working correlation structure more closely approximates the actual correlation structure; therefore, various correlation structures suitable for the study's design will be considered (e.g., exchangeable; nested-1). The QIC statistic will be used to select the final correlation structure. Randomization strata indicators will be included as covariates as required by the stratified randomized design to obtain unbiased inferences. Additional covariates (e.g., HIV serostatus) will be included if they improve QIC. Robust Huber-White "sandwich" standard errors will be used to obtain correct inferences even if the chosen correlation structure remains slightly misspecified. GEE case deletion diagnostics (e.g.,

DFBetas, Cook's *D*) will be used to investigate whether influential cases are present; if such cases are found, results will be reported with and without influential cases included.

**Primary analyses for Specific Aim 2.** For Specific Aim 2, *Elucidate the effects of the Suubi4Her interventions on behavioral health functioning (i.e., depression, self-efficacy and hopelessness) and examine the effects of these variables as potential mechanisms of change, mediating the relationship between each intervention and HIV risk reduction*, we hypothesize that following baseline participants in:

1. H2A: YDA will have higher mean mental health functioning vs. control participants;
2. H2B: YDA+MFG will have higher mean mental health functioning vs. control participants, and
3. H2C: YDA+MFG will have higher mean mental health functioning vs. YDA participants.

[figure not shown]
The same GEE-based approach as described above in the primary analysis for Specific Aim 1 will be used to test H2A-H2C, except that instead of the odds of a binary outcome being estimated, the GEEs for H2A-H2C will employ appropriate distributions and link functions suitable for modeling the means of continuous mental health outcomes (e.g., normal distribution and identity link function). Robust Huber-White "sandwich" standard errors will be used to obtain correct inferences even if the chosen correlation structure remains slightly misspecified or if residual distributions are not perfectly normal or homoscedastic.

**Aim 3: Evaluate the cost-effectiveness of each intervention condition.** Following standard practice of measuring cost-effectiveness of interventions, we will measure costs on a per person basis. The intervention costs will include all program costs, including not just the YDA savings match, but also all costs incurred for running the program. Research costs will not be included. Data on the savings match costs will be readily available from the management information system. Data on costs of other program elements will be drawn from project administrative records and collected throughout the intervention period. In the analyses, costs from multiple years will be adjusted for inflation, depreciation, and discounting.

We will estimate how much *Combined Intervention (YDA + MFG)* vs *YDA-alone* increased particular outcomes, such as schooling. The per-person costs of *YDA + MFG*, and *YDA alone* will then be divided by the relevant effect sizes to produce estimates of cost-effectiveness.

**Dissemination.** The research team will facilitate learning across stakeholders and maximize use of the evidence generated through dissemination meetings. Uganda is one of only a few SSA countries which have Child and Adolescent Mental Health (CAMH) policy guidelines developed. Ugandan policy recognizes the burden and impact of poor mental health functioning on children, their families, and communities. If findings warrant, this study will leverage these policy guidelines to maximize dissemination of study findings.

**Timeline.** The first 6 months will be spent hiring and training project staff, preparing study sites, screening and recruitment of participants, as well as refinement of the intervention and assessment protocols. During the next 10 months, we will conduct recruitment of participants, baseline assessment and random assignment to the three study arms. We will also concurrently embark on program delivery, including opening the YDA accounts, launching the MFGs, and financial management trainings. Intervention delivery will continue through month 24. Baseline assessments will be conducted during the first 6 months. We will conduct 12, 24, and 36-months post-intervention initiation assessments between months 18-54. We will devote the last 6 months of the study (month 54-60) to data analysis and dissemination of study findings.

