#### **Selection of Participants**

The target population for this study are older adolescent girls (ages 15-17 at enrollment), in secondary school and living within the four districts of Uganda: Masaka, Rakai, Lwengo and Kalungu. HIV prevalence in this region is 9.8%, compared to other regions in Uganda (7.3%).

**Inclusion Criteria:** Specifically, for an adolescent to be included in the study, she will have to meet the following criteria: (1) female; (2) enrolled in her first year of secondary school (senior

1) in Rakai, Masaka, Lwengo or Kalungu districts; (3) age 15-17 years; (4) living within a family (broadly defined and not an institution or orphanage, as those in institutions have different familial needs).

**Exclusion criteria:** Girls are ineligible if: (1) they have a cognitive or severe psychiatric impairment that would prevent comprehension of study procedures as assessed during the Informed Consent process (see Recruitment and Consent Section) or; (2) they are unwilling or unable to commit to completing the study.

We will not exclude girls because of their HIV, STI and/or pregnancy status and the analysis will be adjusted to account for these baseline factors. Girls testing positive for HIV, STI (Gonorrhea, Trichomonas, or Chlamydia) or pregnancy will be referred for care and support (see *Study Population* above). A plethora of services, including access to free antiretroviral therapy (ART), and counseling exist for children and adults living with HIV in the study region. We will follow up with all girls who test positive for HIV or an STI within 30 days of referral, to check on their engagement in care. For girls who test HIV positive, engagement in care will be verified annually using clinical and viral load records.

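### Aim 1 sets a population-average target, but its covariate-adjusted logistic GEE gives a covariate-conditional odds ratio and no step averages it back

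*Combined protocol and SAP*

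**What the plan says.** All of the following is in Data Analysis Plan and Statistical Procedures unless another section is named.

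- Target: "Our primary interest is to estimate the marginal or population-average effects of intervention participation on HIV risk outcomes", and the sentence continues "rather than the effect for a hypothetical average subject or school". The contrast drawn is the usual one between GEE and random-effects models.
- Scale: the hypotheses concern odds, for example H1A, "YDA will have lower odds of STIs and HIV risk behaviors vs. control participants".
- Model: "The alternating logistic regression (ALR) approach implemented in SAS PROC GENMOD will be used".
- Contrast: "These hypotheses will be tested by three pairwise planned time-averaged comparisons of post-baseline measurements".
- Covariates always in the model: "Randomization strata indicators will be included as covariates as required by the stratified randomized design to obtain unbiased inferences". The strata are not named.
- Covariates that depend on the data: "Additional covariates (e.g., HIV serostatus) will be included if they improve QIC".
- In Selection of Participants, on baseline HIV, STI and pregnancy status: "the analysis will be adjusted to account for these baseline factors". No QIC condition is attached there.

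Neither section describes standardization, an unadjusted primary estimate, or a fixed list of covariates.

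**The concern.** GEE averages over the correlation within girls and within schools. It does not average over covariates placed in the linear predictor. Odds ratios are non-collapsible: even with perfect balance between arms, an odds ratio given a prognostic covariate differs from the one formed from the arm-level risks. The plan leaves this second kind of conditioning unaddressed.

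What is at stake is the meaning of the reported effect size. It would depend on which covariates enter, and the QIC rule leaves that open until the data are seen. If the sets differed between STI and behavioural outcomes, their odds ratios would not be directly comparable. A conditional odds ratio also does not give the absolute risk change, which would be needed if an Aim 1 outcome entered the Aim 3 ratio of cost to effect size.

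**Working it through.** The plan gives no outcome rate, effect size or power figure, so there is no figure of its own to reproduce. The check asks how far the conditional and marginal odds ratios differ over stated ranges.

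**Inputs from the documents.** 1260 girls; regional HIV prevalence 9.8% (Selection of Participants), used as a high value for girls aged 15-17.

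**Assumptions.** Conditional arm odds ratio .60; control risk p0 from 5% to 40%; covariate prevalence q and covariate odds ratio k as shown; covariates independent of arm.

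**Formula.** Let u be the control-arm odds when the covariate is absent.
1. Solve (1-q)·u/(1+u) + q·ku/(1+ku) = p0 for u.
2. p1 = (1-q)·.6u/(1+.6u) + q·.6ku/(1+.6ku).
3. Marginal OR = [p1/(1-p1)] / [p0/(1-p0)].

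**Example by hand** (p0 = .40, q = .30, k = 5).
- u = .40: .70 × .40/1.40 + .30 × 2/3 = .20 + .20 = .40.
- p1 = .70 × .24/1.24 + .30 × 1.2/2.2 = .1355 + .1636 = .2991.
- Marginal OR = (.2991/.7009)/(.40/.60) = .4268/.6667 = .640.
- Ratio of log odds ratios: ln .60 / ln .640 = .511/.446 = 1.15. The conditional log odds ratio is about 15% larger.

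**HIV serostatus at 9.8%.**
- k = 3, p0 = .20: u = .2177 and p1 = .902 × .1155 + .098 × .2816 = .1318, so marginal OR = .1518/.25 = .607.
- k = 10, p0 = .20: u = .1792 and p1 = .902 × .0971 + .098 × .5182 = .1384, so marginal OR = .1606/.25 = .642.
- Over k = 2 to 10 and p0 = 5% to 40%, the range is .601 to .642.

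**The three named baseline factors together.** Assume they are independent: HIV 9.8% with k = 3, STI 20% with k = 5, pregnancy 5% with k = 3. The same formula, summed over the eight combinations, gives at p0 = .40: u = .4036, p1 = .2993, marginal OR = .4271/.6667 = .641. At p0 = .05: u = .0238, p1 = .0313, marginal OR = .614.

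**A single strong predictor, and one weak one for comparison.**

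| p0 | q | k | Marginal OR | Conditional / marginal log OR |
|---|---|---|---|---|
| .05 | .30 | 10 | .615 | 1.05 |
| .10 | .30 | 10 | .630 | 1.11 |
| .20 | .20 | 5 | .627 | 1.09 |
| .20 | .30 | 10 | .657 | 1.22 |
| .40 | .20 | 5 | .632 | 1.11 |
| .40 | .30 | 10 | .679 | 1.32 |
| .30 | .05 | 3 | .605 | 1.02 |

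**Does standardizing recover the target?** One simulated data set had 4000 schools of 30 girls, three visits, arm assigned by school, and a covariate with SD 1 on the logit scale. It was fitted by logistic GEE with independence working correlation. The unadjusted OR was .574 and the adjusted coefficient gave .529. Standardized risks from the adjusted model were .211 and .318, so the OR was (.211/.789)/(.318/.682) = .574. Standardizing returns the population-average value; the adjusted coefficient does not.

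**Does it affect the tests?** A conditional OR of 1 gives p1 = p0 in the formula, hence a marginal OR of 1. In 400 simulated null trials of 28 schools, rejection at .0167 was 4.75% unadjusted and 4.5% adjusted, so adjustment made no material difference. Both rates exceed .0167 because the simulation used an uncorrected sandwich variance with 28 schools, under assumed variance components. That is a separate matter from this point.

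**The case against.** The strongest reply is that the plan defines its own term. Marginal is set against subject-specific and school-specific effects, and a covariate-adjusted GEE odds ratio is marginal in that sense. This stands: a reader might infer that the plan contradicts itself, and the text does not support that. What remains is a gap. The plan also calls its target population-average, and an odds ratio given covariates is not an average over the girls.

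Other parts of the reply also stand:

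- A reader might infer that the tests of H1A to H1C are invalid. They are not, because the null hypotheses coincide.
- A reader might infer that each outcome will carry a different covariate set. The plan does not say so. QIC is computed for each fitted model and nothing fixes a common set, so it is possible but not stated. Likewise, that the adjusted contrast is the reported effect is inferred from the absence of any further step.
- An adjusted odds ratio is a valid estimate of a different quantity, so it is too strong to say that it exaggerates the effect.
- For HIV serostatus, the only covariate named in the Data Analysis Plan, the shift is negligible to modest. The larger figures need a strong predictor whose prevalence and strength the documents do not give.
- The hypotheses are stated as odds, so non-collapsibility does not require making a risk difference primary or moving the tests to it.

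**Conclusion.** The point holds for the binary Aim 1 outcomes, as a matter of what the reported effect size means. The model conditions on strata and admitted covariates, and nothing returns the contrast to a population average. When the effect is non-null, the odds ratio is further from 1 than the population-average one and depends on the covariate set.

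For an assumed conditional odds ratio of .60, the marginal value is about .60 to .64 with the named covariates, so the conditional log odds ratio is at most about 15% larger. It reaches about .68 (32% larger) with a predictor of 30% prevalence and odds ratio 10 at a control risk of 40%. Baseline STI status could be a strong predictor of later STI, but the documents give no figure for it. Aim 2 is unaffected under the identity link the plan gives as its example, because mean differences are collapsible.

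**What to change.** - Prespecify one covariate set for all Aim 1 outcomes. Reconcile the unconditional adjustment in Selection of Participants with the QIC rule in the Data Analysis Plan.
- Keep the adjusted GEE and its tests of H1A to H1C on the odds scale.
- From that model, predict each girl's risk under each of the three arms at her own baseline covariates, averaging over the post-baseline visits. Average over all 1260 girls, and report the marginal odds ratio as the effect estimate with the marginal risk difference alongside.
- Take variances from a delta method clustered on school or a leave-one-school-out jackknife.

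The cost is a few lines of code and some SAP wording. The drawback is that reported odds ratios will be slightly closer to 1.

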Adolescents will be consented separately from their caregivers. An adolescent to be included on the list of interested participants will sign a standard assent form. The Project Coordinator and either the PI ([name]) or Co-I ([name]) or research assistant will read and explain the form to the adolescent, and at the end of each section will solicit and answer any questions from the adolescent. During the consent process, the Project Coordinator or research assistant and either the PI ([name]) or Co-I ([name]) will explain the study procedures to the adolescents. After the Project Coordinator and either the PI or Co-I are assured that the adolescent fully understands what would be expected of her and the caregiving family, the adolescent would be allowed to sign the informed assent form.

In both the consent and assent forms, it will be clearly stated that the adolescent can withdraw from the study at any time, for any reason, with no explanation, and would not be penalized in any way. It will state that a participant may refuse to answer any questions at any time, may review any materials, may request that we erase any of their responses and may make inquiries and address complaints to Executive Secretary, Uganda National Council for Science and Technology, Chair of UVRI Research and ethics committee or Chair of the Washington University's Committee for the Protection of Human Subjects. As mentioned earlier, the research team will also inform the participant of any potential risks and benefits of participating in the program. Each participant will receive a copy of the assent/consent form, and both the adolescent minor and her caregiver will be thoroughly briefed regarding the importance of assent/consent being both informed and voluntary.

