### **Potential Risks**

There are no major risks involved, however, an adolescent may feel embarrassed or uncomfortable during the recruitment and interview process when answering sensitive and personal questions, with urine collection for pregnancy testing, taking blood for HIV and/or high vaginal swabs for STIs (Gonorrhea, Trichomonas and Chlamydia). The process of blood draw may cause some discomfort, bleeding, or bruising where the needle enters the body, and in very rare cases, fainting or infection. First and foremost, interviewers will make it explicitly known to the participants that they may refuse to answer a question or decline to undergo a procedure, at any time. This will also be explained in writing on the consent/ assent forms. If an adolescent tells the interviewer that she is uncomfortable with a particular topic, that she prefers not to discuss a particular topic, or feels she cannot participate in the biomarker process the interviewer will move on to the next question/part of the interview.

Additionally, for questions measuring sensitive behaviors like sexual risk-taking and mental health, we will use audio computer-assisted self-interviews (ACASI) where the participant takes the survey herself on a mini laptop/iPad. This will provide additional privacy for the participant, can be programmed in multiple languages, and is designed for use by both literate and pre-literate populations. Research assistants will be available for any participant experiencing technical difficulty with the use of the computer-assisted interview.

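### Aims 1 and 2 rest on unweighted GEE with no missing-data method, so loss whose link with the outcome differs by arm can bias the contrasts in either direction

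*Combined protocol and SAP*

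**What the plan says.** Under Data Analysis Plan and Statistical Procedures, "generalized estimating equations (GEE) will be used to perform the proposed primary analyses to test Hypotheses H1A-H1C", through "three pairwise planned time-averaged comparisons of post-baseline measurements". On fitting, "The alternating logistic regression (ALR) approach implemented in SAS PROC GENMOD will be used"; on structure, "The QIC statistic will be used to select the final correlation structure". The reassurance offered is "Though GEE estimates are consistent even if the correlation structure is misspecified", together with sandwich standard errors. Aim 2 uses the same approach for continuous outcomes. The only robustness check is case deletion for influential observations.

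Nowhere do the documents give an expected loss, an analysis set, an assumed missing-data mechanism, weights, imputation or a sensitivity analysis. They do foresee missing outcomes:

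- Recruitment and Consent states that "the adolescent can withdraw from the study at any time, for any reason, with no explanation", and lets a participant have responses erased.
- Potential Risks says that if a girl "feels she cannot participate in the biomarker process the interviewer will move on to the next question/part of the interview".
- Protection from Potential Safety/Clinical Risks halts involvement after adverse events, which include abuse in the family and worsening mental health. It does not say whether outcome assessment stops too.

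Selection of Participants promises adjustment for baseline HIV, STI and pregnancy status. The analysis plan admits additional covariates, with HIV serostatus as its example, only if they improve QIC.

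**The concern.** Neither robustness property that the plan cites deals with who is missing. A misspecified correlation leaves GEE consistent, and the sandwich estimator corrects standard errors, but both take the observed outcomes as representative given the covariates in the model. Girls who are sexually active, pregnant or in distress may be the ones who decline a test or are lost.

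What matters for the arm contrasts is whether that link between risk and loss differs by arm. It could. Savings-arm girls have a match of up to US$240, the combined arm adds 18 family sessions, and control girls have neither. Adverse-event halting also acts on events that overlap the Aim 1 violence outcome and the Aim 2 mental health outcomes. If the link differs, the three planned odds ratios and the three mean differences are biased. The limit of the estimate then also depends on the working correlation, so the QIC choice partly sets the answer.

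**Working it through.** **The plan's own figures.** 0.05/3 = 0.01667, which rounds to the stated 0.017; 3 × 420 = 1260. No power, event rate, ICC or dropout figure is given, so every rate below is an assumption.

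**One visit, by hand.** If a share L1 of positives and L0 of negatives is lost in an arm, its observed odds are the true odds × (1 − L1)/(1 − L0). With L1 = 0.30 and L0 = 0.05 in the treated arm, and 5% of everyone lost in control, a true OR of 1 becomes 0.70/0.95 = 0.74. If both arms have the same L1 and L0, the factor cancels and the OR stays 1. If loss differs by arm but not by outcome, the factor is 1 in each arm.

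At 20% prevalence the selective arm loses 0.2 × 0.30 + 0.8 × 0.05 = 10% and the other 5%, about 8% on average. With 420 per arm, two-sided rejection at 0.017 is then 22% (ICC 0) to 9% (ICC 0.05). With 15% of positives lost it is 3.9% to 2.6%.

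**Three visits, past outcome drives loss.** These are large-sample limits of logistic GEE with visit effects and one arm effect. Inputs: true OR 1, 17% prevalence, random intercept with SD 2 on the logit scale, and monotone dropout that depends on the previous outcome, starting from baseline.

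- Moderate: per-wave loss of 20% after a positive and 5% after a negative in the selective arm; flat 5% in the other.
- Stronger: 30% and 5% in the selective arm; flat 10% in the other.

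Retention at 36 months is 73% to 86% (flat arms: 0.90³ = 0.729 and 0.95³ = 0.857).

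| Pattern | Independence | Exchangeable |
|---|---|---|
| Moderate, selective in treated arm | 0.90 | 0.94 |
| Stronger, selective in treated arm | 0.84 | 0.90 |
| Moderate, selective in control | 1.11 | 1.06 |
| Stronger, selective in control | 1.19 | 1.10 |
| Moderate, treated arm, baseline outcome in model | 0.96 | 1.00 |
| Stronger, treated arm, baseline outcome in model | 0.94 | 0.99 |

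Inverse-probability weighting gives 1.00 in the unadjusted patterns. If first-wave loss does not depend on baseline status, the treated-arm limits shrink to 0.95 and 0.997 (moderate) and 0.92 and 0.99 (stronger), without baseline adjustment.

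**Three visits, other mechanisms.** Inputs: control risk 10/15/20% at 12/24/36 months, 5% loss per visit, rising to 30% where a positive outcome drives loss. Entries are independence / exchangeable.

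| Loss depends on | True OR 1.0 | True OR 0.6 |
|---|---|---|
| Arm only (15% v 5%) | 1.000 / 1.000 | 0.600 / 0.600 |
| Previous outcome, alike in arms | 1.000 / 1.000 | 0.607 / 0.606 |
| Current outcome, alike in arms | 1.000 / 1.000 | 0.607 / 0.606 |
| Previous outcome, control only | 1.083 / 1.010 | 0.650 / 0.609 |
| Current outcome, control only | 1.470 / 1.431 | 0.883 / 0.861 |
| Current outcome, treated only | 0.680 / 0.699 | 0.413 / 0.422 |

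Weights built on arm, visit and previous outcome restore 1.000 and 0.600 in the fourth row. They do not repair the fifth: 1.438 and 0.863.

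**Aim 2.** For a true difference of 0.30 SD, the available-case difference is 0.284 when loss acts alike in both arms and 0.209 when it acts in one arm only; a true 0 then becomes −0.09.

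**Limits of the check.** Standard GEE was used rather than ALR, and school clustering was left out of the limit calculations.

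**The case against.** The strongest reply is that the plan says nothing false and that the damage is conditional. Most of it stands.

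- A reader might infer that the plan claims validity under any missing data. It does not: the consistency sentence is true and limited to working correlation. The fault is an omission. That all available outcomes would simply be used is also an inference, though it is what a fit without weights or imputation does.
- A reader might infer that any departure from missing completely at random, or any outcome-related loss, biases the contrasts. The calculations contradict this: loss by arm alone is harmless, and outcome-related loss alike in all arms moves 0.600 only to 0.607.
- A reader might infer that the bias favours the intervention. If savings keep girls in, selective loss falls in control and the bias runs against the intervention (1.06-1.19). The documents do not settle the direction. Access to the match depends on completing workshops, not on attending assessments.
- The promised baseline adjustment would remove most of the STI bias under an exchangeable structure when past outcomes drive loss. The promise does not name baseline risk behaviours, however, and the analysis plan leaves extra covariates to QIC.
- Independence, which gives the larger figures, is not among the structures the plan names as examples.
- Home assessments, self-interview for sensitive items, exclusion of girls unwilling to commit, and follow-up of girls testing positive should all reduce loss. They do not replace a stated method, and they do not prevent refusal of a swab.

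**Conclusion.** The concern holds as an omission with conditional consequences. Unweighted GEE with no missing-data method is valid for these contrasts only if loss is completely at random or depends only on modelled covariates, and material bias arises when the outcome-loss link differs by arm. That is plausible here but not shown. Under the assumed dropout driven by past outcomes, a true OR of 1 is estimated at about 0.84-0.94 or 1.06-1.19, according to which arm loses selectively. Baseline adjustment with an exchangeable structure brings the treated-arm cases to about 0.99-1.00. Loss that depends on current status in one arm is more serious (0.68 to 1.47 under the assumed rates), and weighting does not correct it. The size in this trial cannot be fixed from the documents. The plan should close the gap before outcomes are analysed.

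**What to change.** 1. State the expected loss per wave and arm, the analysis set and the assumed mechanism.
2. Fit the baseline value of each outcome as a fixed covariate, not subject to QIC. For HIV, STI and pregnancy this also honours the adjustment promised under Selection of Participants.
3. Prespecify an analysis valid under missing at random for H1A-H1C and H2A-H2C. One option is school-clustered GEE weighted by the inverse probability of being observed, estimated by arm and wave from baseline and previous-wave outcomes and strata. The other is multiple imputation that respects the school clusters. Report the unweighted GEE alongside.
4. Add delta-type sensitivity analyses for loss that depends on current status, with the shift varied separately by arm. Handle refusal of a swab or test apart from visit non-attendance.
5. State whether halting involvement after an adverse event also ends outcome assessment, so that such missing values can be classified.

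The cost is SAP text, modest programming and slightly wider intervals. No change to design or sample size is needed.
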